#### TITLE OF THE RESEARCH:

A Pilot-Feasibility of a Home-based Intervention to Reduce Obesity Risk for Bottle-fed Infants

#### **BRIEF TITLE:**

Opaque Bottle Feasibility Study (OBS-F)

#### STATEMENT OF PURPOSE, BENEFITS, AND HYPOTHESES:

Rapid weight gain during the first year of life is a strong and consistent predictor of later development of obesity leading researchers and government bodies to call for obesity prevention efforts starting during infancy. Mounting evidence illustrates that bottle-fed infants (whether fed formula or expressed breast milk) are at significantly greater risk for rapid weight gain, gaining an excess of 70-90 grams/month across the first year when compared to their breastfed peers. While the experience of breastfeeding may help mothers develop feeding practices that are responsive to infant satiety cues because they must learn to trust their infants' developing abilities to self-regulate intake, bottle-feeding may facilitate controlling feeding practices due to mothers' abilities to feed in response to the amount of milk in the bottle, leading to overfeeding and excess weight gain.

Public health efforts to date have focused on breastfeeding promotion programs. Regardless, over 50% of US infants are exclusively formula-fed at 6 months of age. Moreover, 40% of breastfed infants receive supplemental formula in a bottle, and 70% receive expressed breast milk from a bottle on a regular basis. Despite the ubiquity of bottle-usage, mothers receive little to no support for learning healthy bottle-feeding practices and a paucity of research has focused on improving bottle-feeding mothers' responsiveness to infant cues. Previous efforts have focused on educating mothers about infant cues and offering less formula during each feeding, but have shown little success in modifying feeding behaviors or weight gain outcomes. Thus, promotion of healthy bottle-feeding practices remains a realistic but under-utilized facet of obesity prevention efforts.

In the proposed research we take a novel, pragmatic approach to promote healthy bottle-feeding. Our previous research has explored whether a simple intervention - covering bottles with an opaque, weighted sleeve – can improve maternal responsiveness

to infant cues during bottle-feeding. Indeed, in an NIH-funded, laboratory-based trial (R03-HD080730), we illustrated mothers show significantly greater responsiveness and feed their infants 26% less when using opaque, weighted bottles compared to conventional, clear bottles. While initially conceived as a promising adjunct to a larger obesity prevention approach, our laboratory findings suggest that opaque bottles may be a simple, yet potent, stand-alone tool for improving mothers' abilities to feed responsively and reducing infants' risk for overfeeding and rapid weight gain. In the proposed study, we aim to test this approach outside of the laboratory and enroll 100 new, formula-feeding mothers and infants (< 2 weeks old) into a randomized trial to examine the 12-week effects of using opaque, weighted bottles versus clear bottles for improving bottle-feeding interactions and reducing child obesity risk. We will use preestablished and state-of-the-art procedures to objectively measure infants' intake and mothers' responsiveness to infant cues (i.e., objective assessment of feeding patterns, coding of mother-infant bottle-feeding interactions) within their homes at the beginning and end of the 12-week study period. Intervention feasibility, fidelity, acceptability, and safety will be evaluated. Specific aims of the proposed research are:

AIM 1: To test the hypothesis that mothers who use opaque, weighted bottles for a 12-week intervention period will feed their infants less and be more responsive to their infants' cues compared to mothers who use clear bottles. Intake will be objectively assessed via change in bottle weight before and after feeding observations. Responsiveness to infant cues will be coded from video-records of feeding observations using the Nursing Child Assessment Parent-Child Interaction Feeding Scale.

AIM 2: To test the hypothesis that infants who are fed from opaque, weighted bottles will exhibit slower 12-week weight gain trajectories compared to infants who are fed from clear bottles. Infants' weight, length, skinfolds, and waist circumference will be measured at the beginning and end of the study; weight-forlength z-scores (WLZ) will be calculated using the WHO Growth Standards.

AIM 3: To examine the feasibility, fidelity, adherence, acceptability (e.g., perceived barriers to use), and safety (e.g., feeding adequacy) of the opaque, weighted bottle intervention. We will collect both objective and subjective data related to bottle use. We will also assess mothers' perceptions of the opaque bottles, any perceived barriers to their use, and whether baseline characteristics of mothers (e.g., weight status, race/ethnicity, socioeconomic status, parity, other non-maternal caregiver feeding practices and styles) and infants (e.g., sex, weight status, temperament) moderate intervention effects.

The proposed study is a critical step toward understanding the potential for opaque, weighted bottles as a practical solution for reducing obesity risk during infancy. Additionally, given the demographics of our community (35% Hispanic; 34% minority races), we have the opportunity to test this intervention in a diverse sample that includes a large proportion of families of lower socioeconomic status, two major risk factors for unhealthy bottle-feeding practices and childhood obesity.

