#### **Assessments and Measures**

As illustrated in the **Table**, we will conduct two assessments (separated by one day) at both study entry and completion to objectively measure infant intake and maternal responsiveness. Two brief visits will occur at weeks 2 and 6 to assess infant growth and maternal adherence to the intervention. All assessments will be administered by blinded research assistants.

Study Week:	1	1	2	6	12	12
Assessment Type:	Pre- Test 1*	Pre-Test 2*	Brief visit for	Brief visit for	Post-Test 1*	Post- Test 2*
Bottle used during observation: Clear Bottle Group	Clear	Opaque	growth check	check	Opaque	Clear
Opaque Bottle Group	Opaque	Clear			Clear	Opaque

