- Maternal responsiveness to infant cues will be objectively assessed by video-coding of all feeding observations. After each visit, three trained coders who are unaware of the experimental conditions and hypotheses of the study will code videos using the NCAFS, a reliable and valid means of observing and rating mother-child interactions during a feeding session. The NCAFS is validated for use with mothers and their 0-1-year-old infants, can be applied to a breast or bottle-feeding episodes, and has been used during both lab- and home-based feeding observations. It contains 76 observable behaviors that are organized into six subscales; for the proposed research, we will

focus the Maternal Sensitivity to Infant Cues subscale. Reliability will be established prior to full coding of all videos. To this end, coders will code 10 common videos, and will double-code 10 additional videos. Inter-coder comparison of the 10 common videos will be used to establish inter-coder reliability. Intra-coder comparison of the 10 double-coded videos will be used to establish intra-coder reliability. Full coding will not commence until a Kappa > 0.80 is reached for all coders. The PI is certified in this coding system and has it previously.

- Maternal feeding style, including responsive and pressuring feeding, will also be subjectively assessed at study entry and completion using the Infant Feeding Style Questionnaire (IFSQ; see Appendix 4), which assesses maternal behaviors (e.g., control) and beliefs (e.g., concern about feeding) related to infant feeding. This scale has been validated in diverse samples of mothers with young infants and the PI has used this measure in previous research.
- Infant growth will be assessed during all home-based assessments by trained research assistants measuring infant weight and height in triplicate using a portable infant scale/infantometer (models 334 and 233; Seca, Hamburg, Germany). To minimize bias, infants will always be weighed and measured while only wearing a clean diaper and prior to the observed feeding. We will use the World Health Organization (WHO) Anthro software version 3.0.1 (http://www.who.int/childgrowth/en/) to calculate age-and sex-specific weight-for-length z-scores (WLZ) based on the WHO growth standards. We will also assess infant adiposity by infant skin-fold thickness and waist circumference using standard protocols.

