#### **Statistical Considerations**

Data Analysis. All quantitative analyses will be conducted using SAS v.9.4 (SAS Institute Inc., North Carolina, USA). Oualitative interview data will be transcribed and sorted into thematic categories using constant comparison within the framework of grounded theory. We will use linear regression to model the change in infant intake and maternal responsiveness (Aim 1) and change in WLZ, skinfolds, waist circumference (Aim 2) by the primary study variable of *clear* versus *opaque* group. For Aim 3, we will examine the feasibility, fidelity, adherence, acceptability, and safety of the intervention by summarizing quantitative and qualitative data related to recruitment and retention, mothers' use of their assigned bottles, perceptions of and barriers to using the bottles, and any issues related to infant inadequate weight gain or weight loss. We will then explore whether variations in intervention feasibility, fidelity, adherence, acceptability or safety are correlated with baseline characteristics of mothers (e.g., weight status, race/ethnicity, socioeconomic status, parity, feeding practices and styles, non-maternal caregiver involvement in feeding) and infants (e.g., sex, birth weight, weight status, temperament). Finally, we will assess whether the effects of the intervention on infant intake, maternal responsiveness, and infant WLZ change are moderated by the following factors: nipple type; mothers' adherence to the intervention, race/ethnicity, parity, or feeding practices and styles; infants' sex, temperament, and timing of solid food introduction; and the extent to which non-maternal caregivers are feeding the infant. Moderation will be explored by including a group by moderator interaction term in the linear regression models used to explore Aims 1 and 2. All inferential analyses will be preceded by appropriate descriptive statistics and graphs to determine that assumptions for linear regression are satisfied.

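### Aim 2 hypothesises slower weight gain, but its only weight-based outcome is a two-point change in weight-for-length z-score, and no between-arm comparison of weight gain or length growth is planned

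*Combined protocol and SAP*

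**What the plan says.** The hypothesis under Aim 2 is that "infants who are fed from opaque, weighted bottles will exhibit slower 12-week weight gain trajectories compared to infants who are fed from clear bottles". The rationale earlier in the same section is also about weight: bottle-fed infants are described as "gaining an excess of 70-90 grams/month across the first year when compared to their breastfed peers".

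The measurement sentence under Aim 2 reads "Infants' weight, length, skinfolds, and waist circumference will be measured at the beginning and end of the study". The one z-score to be derived, according to the infant growth item under Assessments and Measures, is "age-and sex-specific weight-for-length z-scores (WLZ) based on the WHO growth standards".

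Under Statistical Considerations, the Data Analysis paragraph applies linear regression to "change in WLZ, skinfolds, waist circumference (Aim 2) by the primary study variable", that is, by randomised group. The Power calculations paragraph gives a detectable difference of 0.59 in WLZ change between baseline and week 12. It calls this clinically significant by reference to a definition of rapid weight gain as a z-score change of at least 0.67 SD, without saying which z-score that definition uses.

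There are interim growth data: "Two brief visits will occur at weeks 2 and 6 to assess infant growth and maternal adherence to the intervention". No named analysis uses them.

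Safety is handled separately. The monitoring plan watches each infant for gain below 20-30 g/day or for weight loss, with quarterly review by the safety monitor, referral and possible removal from the study. Aim 3 summarises problems of inadequate gain or weight loss.

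**The concern.** The quantity in the hypothesis and the quantity in the analysis are not the same. The hypothesis is about weight gain over 12 weeks. The analysed outcomes are one index of weight relative to length and two measures of adiposity. An infant who gains less weight and also grows less in length can keep the same WLZ, so a real slowing of weight gain could be reported as a null Aim 2 result.

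The same gap matters for growth safety at group level. The protocol reports that infants were fed 26% less from opaque bottles in the laboratory, and it recognises underfeeding with inadequate growth as a possible unintended consequence. A moderate slowing of both weight and length across the opaque arm would show in no planned between-arm z-score.

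Finally, the hypothesis speaks of trajectories, while the planned contrast uses only the first and last time points.

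**Working it through.** **Inputs from the Power calculations paragraph.** n = 100, SD of WLZ 1.0, correlation over 12 weeks r = .45, power 80%, α = .05. Assumptions: 1:1 allocation (50 per arm) and a two-sided test; the documents state neither.

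**Step 1. Reproduce the plan's figure.**
- SD of change = 1.0 × √(2 × (1 − 0.45)) = √1.10 = 1.049.
- Standard error of the difference = 1.049 × √(2/50) = 0.210.
- Detectable difference = (1.960 + 0.842) × 0.210 = 0.588; with the t distribution, 0.594.

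This matches the stated 0.59. Other designs do not: one-sided gives 0.52, baseline-adjusted 0.50, week 12 only 0.56. The powered Aim 2 contrast is therefore a two-point change in WLZ.

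**Step 2. Power if only part of the weight effect reaches WLZ.** Let the true slowing of weight gain be worth 0.59 SD, or 0.67 SD (the protocol's rapid-gain benchmark), and let a share f of it appear in WLZ. The noncentrality is f × effect / 0.210. Power uses the two-sided t test with 50 per arm.

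| Share f appearing in WLZ | Power, true effect 0.59 | Power, true effect 0.67 |
|---|---|---|
| 1.00 | 80% | 88% |
| 0.75 | 55% | 66% |
| 0.50 | 29% | 35% |
| 0.25 | 11% | 12% |
| 0 | 5% | 5% |

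The documents do not give f, so the table is a range and not a prediction.

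**Step 3. What a direct weight outcome would need.** If weight-for-age z-score had the same SD (1.0) and correlation (.45), Step 1 applies unchanged and its detectable difference is also 0.59 at n = 100. Under that assumption it needs no larger sample.

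**Step 4. What the interim visits add.** For a slope over weeks 0, 2, 6 and 12, expressed as a 12-week difference, the detectable value is 0.54 if all pairs of visits correlate at .45. It is 0.59 if correlation decays with time to .45 at week 12. Against 0.59 for two points, the gain in precision is small.

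**The case against.** The strongest reply is that Aim 2 names WLZ immediately after the hypothesis, that the study's purpose is obesity risk, and that WLZ, skinfolds and waist circumference are reasonable adiposity outcomes for a pilot. Rewording Aim 2 as change in WLZ would remove the mismatch without adding outcomes to a plan that ranks none. This stands as a minimum remedy, but it would leave the trial with no randomised answer on weight gain, which is what its rationale is about.

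A reader might go further and infer that a growth harm would be missed outright. The documents do not support that. Monitoring uses absolute gain in g/day and weight loss, neither of which depends on WLZ. Referral and possible removal follow, and Aim 3 reports such problems. A marked problem in one infant would be seen. Nor is underfeeding presented as the leading risk: it is one of several listed, and overall risk is called minimal.

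A reader might also take the 70-90 g/month excess and argue that an effect of that size would vanish in WLZ. That figure compares bottle-fed with breastfed infants across the first year, not opaque with clear bottles over 12 weeks. The documents give nothing on how far length would slow. They also place the emergence of feeding-mode differences in weight at 12 to 24 weeks.

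Two smaller points stand. Weight and length are specified for the home-based assessments, which the Design paragraph separates from the brief ones; the brief visits assess growth, but length is not expressly mentioned. And no missing-data rule is stated, so the loss of infants who leave after week 6 follows from using a baseline-to-week-12 change and is not declared policy.

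**Conclusion.** The concern holds in a limited form. The weight-gain hypothesis has no weight-gain analysis, and the outcome that stands in for it can understate or hide the effect if length slows too. For a true 0.59 SD effect with 50 per arm, power lies between 80% and 5%, and is about 29% if half the effect appears in WLZ. This rests on the protocol's SD and correlation, equal allocation, a two-sided test and a share that the documents do not supply.

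On safety, the gap is the absence of a between-arm comparison of weight gain and length growth, not an absence of monitoring. A direct weight outcome would match the hypothesis; it would not by itself secure power for a true effect smaller than 0.59 SD. The point should be addressed, since the data for the main change are already planned.

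**What to change.** In the Aim 2 statement and the Data Analysis paragraph:

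- Add change in weight-for-age z-score, reported together with weight gain in g/day, as the Aim 2 weight-gain outcome.
- Keep WLZ, skinfolds and waist circumference, labelled as adiposity outcomes.
- Report a between-arm comparison of change in length-for-age z-score from entry to week 12 as a growth-safety outcome.
- Fit a repeated-measures model that includes the week 2 and week 6 weights, and lengths if they are taken, so that the analysis describes a trajectory and keeps infants who leave after an interim visit. State whether length is measured at those visits.

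The entry and week 12 analyses need no new visit or measurement: weight and length are already taken, and age and sex are needed for the planned growth-standard scores. The cost is wording, some analysis, and one or two more outcomes to report and rank. The repeated-measures model is justified by its fit to the hypothesis and its use of partial data, not by its small gain in precision. If the sponsor does not want further outcomes, Aim 2 should at least be reworded to claim only an effect on WLZ and adiposity.

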#### **METHODS:**

#### **Design and Sample**

Design. We have designed a 12-week randomized clinical trial to explore the efficacy

and feasibility of a 12-week opaque, weighted bottle intervention. Previous research suggests that, during early infancy, 12 weeks is a sufficient duration of follow-up to capture divergences in growth trajectories related to feeding mode, and that the window between 12-24 weeks is when associations between feeding mode and excess weight gain emerge. Mother-infant dyads will be randomized to use conventional, clear bottles (*clear* group) or opaque, weighted bottles (*opaque* group). Dyads will participate in home-based assessments of bottle-feeding interactions at study entry and 12 weeks, with brief assessments at 2 and 6 weeks.

**Subjects and Recruitment.** A total of 100 mother-infant dyads will participate. We will use recruitment methods similar to those effectively used in our previous research. Mothers will be recruited through ads in local newspapers; targeted social media ads; Women, Infant & Children (WIC) offices; OB/GYN and pediatrician offices; mass mailings; online sites; and a list of past participants who have asked to be notified of future studies. See **Appendix 1** for example recruitment materials.

Given San Luis Obispo and Santa Barbara Counties are predominately White and Hispanic (66% White, 35% Hispanic, 2% Black, and 4% Asian), we will over-sample Black mothers to increase sample diversity (targets: 55% White, 35% Hispanic, 13% Black, 4% Asian). Both English and Spanish-speaking mothers and their healthy, term infants of either sex will be eligible.

Inclusion criteria for the dyads include:

- 1) mothers 18-40-years of age
- 2) infants <8-weeks of age
- 3) mother is planning to bottle-feed, or is currently bottle-feeding, her infant
- 4) mother predominantly or solely responsible for infant feeding
- 5) dyad has a pediatrician and plans to attend infant well-visits
- 6) mother is willing to use stainless-steel bottles and to provide the study will her current bottles, which would be returned after study completion
- 7) prior to the introduction of solid foods

To protect infants who might be at risk for underfeeding or inadequate growth, exclusion criteria for infants include known risk factors:

- 1) preterm birth (i.e., gestational age <37 weeks)
- 2) low birth weight (<2500 g)
- 3) maternal smoking during pregnancy
- 4) current or past medical conditions that interfere with oral feeding
- 5) history of slow growth or failure to thrive
- 6) weight for length percentile  $<5^{th}$
- 7) diagnosed developmental delay (e.g., Down's syndrome)

While we anticipate this will be rare, any mother reporting that they typically use opaque bottles prior to entry will also be excluded.

Research assistants will provide study information to mothers who respond to our recruitment efforts. Mothers who express interest in participating in our study will be screened by trained research assistants to assess study eligibility (see **Appendix 2** for screening and telephone scripts).

**Procedures to Retain Sample.** To promote retention, we will conduct home-based assessments to minimize participant burden. We will compensate participants a total of \$100 (2 pre-test assessments @ \$20 each, 2 brief intermediate assessments @ \$10 each, and 2 post-test assessments @ \$20 each; see **Table**).

**Randomization.** Mothers will be randomized using a computer-generated randomization scheme. Mothers will be informed of the group to which they are randomized by unblinded research assistants at the end of the Home-Based Pre-Test 2 (see **Table**).

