### Table. Example Assessment Timeline and Type of Bottles Used during Feeding Observations

\*Home-based assessments within the same week will be separated by one day; conditions will be counterbalanced.

Home-Based Assessments. Two research assistants will visit the mother's home in the morning (to control for infants' circadian rhythms and variations in intake) and will arrive approximately one hour prior to a time when an infant typically takes a bottlefeeding. Mothers will be asked to hide all bottles prior to each visit to ensure research assistants remain blinded. We will call the mother the evening before each visit to assess whether any disruptive events that may negatively influence the infant's behavior (e.g., colds, teething) occurred; if a disruptive event is reported during this phone call, the visit will be rescheduled. After a short acclimation period, we will interview the mother about when the infant last fed and slept and will conduct additional assessments. When the mother and infant are ready to feed, we will set-up two video cameras (GoPro Hero 4, California, USA) at two different angles (to obtain clear views of both the mother and the infant) ~10 feet in front of a location where the mother typically bottle-feeds her infant and will record the mother feeding her infant using clear or opaque bottles. The mother will be instructed to feed her infant as she normally would at home and the research assistants will wait in another room to minimize any possible influence on the mother's or infant's feeding behaviors. Additional questionnaires will be completed after feeding.

**Measures.** We will evaluate our intervention along multiple dimensions to fully understand the impact of opaque bottles on feeding outcomes and the feasibility of scaling this intervention for larger trials.

- **Infant intake** will be assessed by weighing the infant's bottle before and after each feeding observation using a top-loading balance (SP601 Scout Pro Portable Balance, Ohaus, New Jersey, USA). We will also note the type of nipple used and will control for nipple flow rate in all analyses.

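### Entry age is limited to under 2 weeks in the purpose statement but under 8 weeks in the inclusion criteria, and age at entry is not in any planned model

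*Combined protocol and SAP*

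**What the plan says.** The Statement of Purpose, Benefits, and Hypotheses says the study will "enroll 100 new, formula-feeding mothers and infants (< 2 weeks old) into a randomized trial". Under Methods, Design and Sample, the second inclusion criterion is "infants <8-weeks of age". Both stand in the current text, and no section explains the difference.

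On timing, the Design paragraph says "Dyads will participate in home-based assessments of bottle-feeding interactions at study entry and 12 weeks". It supports this schedule by stating that 12 weeks is long enough to see growth diverge, and that "the window between 12-24 weeks is when associations between feeding mode and excess weight gain emerge".

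On allocation, "Mothers will be randomized using a computer-generated randomization scheme". No stratification factor or allocation ratio is given.

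On analysis, Statistical Considerations specifies linear regression of change in intake, responsiveness, WLZ, skinfolds and waist circumference "by the primary study variable of *clear* versus *opaque* group". The Measures section adds, under infant intake, that the study "will control for nipple flow rate in all analyses"; this is the only covariate named for all analyses. Infant age at entry is not among the moderators in Aim 3, in the Measures section or in Statistical Considerations. The Measures section describes WLZ as specific to age and sex. It states no age standardisation for intake in mL, the NCAFS score, skinfolds or waist circumference.

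**The concern.** The entry-age limit defines who the results apply to, and the two statements differ fourfold. A reader of the protocol cannot tell which infants the trial is meant to represent.

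The limit also sets the spread of ages in the analysis. If intake per feed, feeding behaviour or body measurements change at a rate that depends on the infant's age at entry, a wider range adds variance to the change scores. It also leaves more room for the arms to differ in age by chance. The plan has no term that would absorb either effect in the outcomes without age standardisation. The power statement names no age range, so it does not show whether this variation was allowed for.

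**Working it through.** **Inputs from the documents.** Entry limits of 2 and 8 weeks; final assessment at 12 weeks; n = 100; α = .05; intake SD 33.7 mL; correlation between baseline and 12 weeks of .55 (clear) and .40 (opaque); stated detectable intake difference 19.1 mL at 80% power.

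**Assumptions.** Equal allocation, 50 per arm; two-sided test; entry age uniform from birth to the limit; slopes of intake change on entry age of 2, 5 and 10 mL per week. The documents give no slope.

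1. **Reproduce the plan's intake figure.** SD of change = SD × √(2(1 − r)).
   - Clear: 33.7 × √0.90 = 31.97 mL. Opaque: 33.7 × √1.20 = 36.92 mL.
   - SE of the difference = √((31.97² + 36.92²)/50) = 6.91 mL.
   - Detectable difference = (1.960 + 0.842) × 6.91 = 19.35 mL, against 19.1 mL stated. Power at 19.1 mL is 79.0%. The stated figure is reproduced closely enough to serve as the reference.

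2. **Age at the final visit.** Entry age plus 12 weeks gives 12 to <14 weeks under the 2-week limit and 12 to <20 weeks under the 8-week limit.

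3. **Spread of entry age.** SD of a uniform variable = width/√12: 2/√12 = 0.58 weeks; 8/√12 = 2.31 weeks.

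4. **Chance imbalance in mean age between arms.** SE = SD × √(2/50).
   - 2-week limit: 0.115 weeks; × 1.96 = 0.23 weeks.
   - 8-week limit: 0.462 weeks; × 1.96 = 0.91 weeks.

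5. **Effect on intake without adjustment.** Age adds (slope × SD of age)² to the variance of change in each arm. For example, with 10 mL per week and the 8-week limit, the added variance is (10 × 2.309)² = 533. Then SE = √((1022 + 1363 + 2 × 533)/50) = 8.31 mL, the detectable difference is 2.802 × 8.31 = 23.28 mL, and power at 19.1 mL is Φ(19.1/8.31 − 1.96) = 63%.

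| Assumed slope (mL/week) | Detectable difference, <2 weeks (mL) | Power at 19.1 mL, <2 weeks | Detectable difference, <8 weeks (mL) | Power at 19.1 mL, <8 weeks |
|---|---|---|---|---|
| 0 | 19.35 | 79% | 19.35 | 79% |
| 2 | 19.36 | 79% | 19.52 | 78% |
| 5 | 19.42 | 79% | 20.40 | 75% |
| 10 | 19.62 | 78% | 23.28 | 63% |

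The table also assumes that the pilot SD of 33.7 mL does not already include variation due to age. No equivalent range is worked out for the NCAFS score, skinfolds or waist circumference. The documents give no slope for any of them, and no SD for the last two.

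**The case against.** The case on the other side is substantial.

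- **The eligibility list governs.** One statement is narrative and the other is a numbered criterion, and infants under 2 weeks are a subset of those under 8. So these are not two separate trials or populations. That is correct, but the conflict remains: the stated purpose describes a narrower sample than the criteria admit. Whether staff would screen to different limits cannot be judged, because the screening script is not in the text available.
- **Randomisation protects the comparison.** It does. A reader might infer that leaving out age biases the group effect, and the documents do not support that. Only precision, chance imbalance and the definition of the population are affected.
- **Aim 2 already handles age.** For WLZ, the Aim 2 outcome with a power calculation, the plan describes the score as age- and sex-specific. The point is therefore limited to the outcomes with no stated standardisation. Nor do the models contain group alone, since nipple flow rate is to be controlled throughout.
- **The follow-up window.** A reader might infer that the limit decides whether follow-up reaches the 12-to-24-week window. It does not: on either limit follow-up ends inside it, and the protocol separately states that a 12-week duration is sufficient.
- **Body weight.** It is tempting to turn an age imbalance into grams using the 20–30 g/day in the safety plan. That figure is a threshold for insufficient growth, and weight in grams at entry is not an outcome in the planned regressions.
- **The power loss rests on assumed slopes.** This stands. At 2 mL per week the loss is about one percentage point, and the pilot SD may already contain age variation.

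**Conclusion.** The contradiction in the entry-age limit is certain from the text, and the two statements must be reconciled. The documents do not show which is intended. It is equally clear that age at entry is not a named covariate, moderator or stratification factor.

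The statistical consequence is conditional. With uniform entry ages and 50 per arm, the 95% limit for chance imbalance in mean age is about four times as large under the wider limit: 0.91 against 0.23 weeks. For intake, the loss of power at 19.1 mL ranges from negligible to material (79% down to 78–63%). That range depends on a slope the documents do not give, and on the pilot SD not already including age variation. Under the narrower limit the loss is about one point at most. For the NCAFS score, skinfolds and waist circumference the same reasoning applies, but its size cannot be given.

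**What to change.** State one entry-age limit and use it in the purpose statement, the inclusion criteria and the screening script. The choice belongs to the investigators.

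In Statistical Considerations, prespecify infant age at entry, in days, as a covariate in the regressions for change in intake, NCAFS score, skinfolds and waist circumference. For WLZ it is optional.

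The cost is a wording correction and one degree of freedom per model. No new data are needed, because infant age must be known to check eligibility and to calculate a WLZ described as age-specific.
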